
 This estimand utilizes the same endpoint, summary measure and target population as the co-primary Hgb estimand. For the intercurrent events of death, randomized treatment discontinuation, use of non-randomized ESA medication for any reason including rescue, and blood transfusions, a 'while on-treatment' strategy will be used. This estimand reflects the effect of daprodustat treatment relative to darbepoetin alfa, while on-treatment and without the use of non-randomized ESA medication or blood transfusions. For this analysis, the primary Hgb analyses and summaries described above will be performed using evaluable Hgb values (see Section 10.6.3). No data will be imputed in this analysis, so a summary of missing data will be provided The LS mean treatment difference, and associated 95% CI from this analysis will be included on a forest plot with the primary Hgb analysis results. The number and percentage of subjects meeting each evaluable Hgb (see Section 10.6.3) exclusion criterion will be summarized by scheduled visit. A tipping point analysis similar to the one described above will be performed as a sensitivity analysis for this estimand using evaluable Hgb values only.
PP Population Analysis

 The while on-treatment evaluable Hgb analysis and summaries described above (with the exception of the missing data summary) will also be performed using the PP population and evaluable Hgb values (see Section 10.6.3). The LS mean treatment difference, and associated two-sided 95% CI from this analysis will be included on a forest plot with the primary Hgb analysis results.
Alternative EP (Week 28-36) Analysis

 The following analyses will be repeated using an alternative EP from Week 28-36: 
 The primary analysis and summaries (using on- and off-treatment, observed and imputed Hgb values (see Section 10.6.3))

CONFIDENTIAL

201410

Supportive Statistical Analyses

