8.1.2. Additional Secondary Efficacy Analyses

8.1.2.1. Overview of Planned Additional Secondary Efficacy Analyses

[Table 6](#) provides an overview of the planned additional secondary efficacy analyses

CONFIDENTIAL

201410

Table 6 Overview of Planned Additional Secondary Efficacy Analyses

Endpoint	Analysis Population	Absolute							Change from Baseline						
		Stats Analysis			Summary		Individual		Stats Analysis			Summary		Individual	
		T	F	L	T	F	F	L	T	F	L	T	F	F	L
Hgb Variability															
Hgb change from baseline to Week 52 ^{1,2}	ITT									Y	Y		Y		
Hgb change from baseline to Week 52 by subgroup ^{1,2,3}	ITT									Y	Y				
Hgb responders ²	ITT	Y			Y										
Hgb responders by subgroup ^{2,3}	ITT	Y	Y												
% of time Hgb in analysis range ²	ITT	Y			Y										
% of time Hgb in analysis range by subgroup ^{2,3}	ITT	Y	Y												
Time to Rescue															
Time to stopping randomized treatment due to meeting rescue criteria	ITT	Y	Y		Y										

NOTES :

- T = Table, F = Figure, L = Listing, Y = Yes display generated.
- Stats Analysis = Represents TFL related to any formal statistical analyses (i.e. modelling) conducted.
- Summary = Represents TFL related to any summaries (i.e. descriptive statistics) of the observed raw data.
- Individual = Represents FL related to any displays of individual subject observed raw data.

^[1] Analysis will be performed using all available observed and imputed (on and off-treatment) Hgb values.

^[2] Analysis will be performed using evaluable Hgb values only (see Section 10.6.3).

^[3] Subgroup analysis will be only using stratification factors (dialysis type and dialysis start manner).

CONFIDENTIAL

201410

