
 For the secondary analysis of Hgb change from baseline to Week 52, a mixed model repeated measures (MMRM) approach will be used with an unstructured covariance matrix to compare the difference in means between arms. The model will be fitted to Hgb data collected after baseline up to Week 52, excluding values collected during the stabilization period (Randomization date + 1 day to <Week 28). The model will include factors for treatment, time, prognostic randomization stratification factors (as randomized, see Section 0), baseline Hgb and the baseline Hgb by time and treatment by time interaction terms. Analyses will be done with the MIXED procedure in SAS, using the Kenward-Roger option to estimate denominator degrees of freedom and standard errors. This analysis will be performed using all available Hgb values (on and off-treatment) and separately using evaluable Hgb values only (see Section 10.6.3). In the analysis using all available Hgb values, subjects who withdraw from the study before Week 52 are considered to be missing at random and in the analysis using evaluable Hgb values, subjects who permanently discontinue randomized treatment before Week 52 are assumed to be missing at random. For the Hgb responder analysis, mean Hgb during the EP will be defined as in the while on-treatment supportive analysis (Section 10.6.3). Responders will be subjects with a mean Hgb during the EP that falls within the Hgb analysis range of 10-11.5 g/dL. A Cochran-Mantel-Haenszel (CMH) chi-squared test, adjusting for treatment and the prognostic randomization stratification factors (as randomized, see Section 0), will be used to compare the number and % of responders between the treatment groups. For the analysis of % time in range, the method by Rosendaal [Rosendaal, 1993] will be used to calculate the percentage of time (days) a subject's Hgb is below, within and above the Hgb analysis range of 10 to 11.5 g/dL during the EP (Weeks 28-52) (See Section 10.6.3). A van Elteren test (stratified Wilcoxon rank sum test) will be used to compare the percentage of time in range between treatment arms, adjusting for treatment and the prognostic randomization stratification factors (see Section 0). This analysis will be performed using evaluable Hgb values only. Hodges-Lehmann estimate of the treatment difference will be used to assess non-inferiority in % time in range.
Model Results Presentation

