
 For the MMRM analysis of change from baseline in Hgb, an LSMEANS statement will provide adjusted treatment group means and standard errors and a point estimate and two-sided 95% confidence interval for the adjusted mean treatment difference (daprodustat - darbepoetin alfa) at Week 52. The one-sided non-inferiority p-value for this test will be calculated.

CONFIDENTIAL

201410

Additional Secondary Efficacy Statistical Analyses: Hgb Variability

 For the responder analysis, the number and percentage of subjects with mean EP Hgb above, within and below the Hgb analysis range will be summarized by treatment group. For the responder analysis, the number and % of responders by treatment group, difference in response rate (daprodustat – darbepoetin alfa) and two-sided 95% CI using Wald method will be provided along with the one-sided CMH p-value for the treatment group comparison. If the CMH adjusted treatment difference is positive, then the one-sided p-value is $p/2$, and if the CMH adjusted treatment difference is negative, then the one-sided p-value is $1-p/2$, where p is the two-sided p-value from the CMH test. The % time Hgb is above, in and below the Hgb analysis range (10-11.5 g/dL) during the EP will be summarized using mean, standard deviation, minimum, P25, median, P75, and maximum by treatment group. The percent time in range for each treatment group, the stratified Mann-Whitney estimate of the treatment difference (daprodustat - darbepoetin alfa) and associated two-sided 95% CI [Kawaguchi, 2011] will be presented in addition to the one-sided superiority p-value from the van Elteren test. Hodges-Lehmann estimate of the treatment difference (daprodustat-darbepoetin alfa) and associated two-sided 95% CI will be presented.
Model Results Interpretation

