10.4. Appendix 4: Treatment States and Phases

10.4.1. Treatment Phases

Assessments and events will be classified according to the time of occurrence relative to treatment start and stop dates and last non-zero dose date (see Section 10.6.1).

10.4.1.1. Treatment States for Hgb, Iron Parameters, IV Iron Dose Endpoints, Iron Use Summaries, Transfusion and PRO Data

Treatment Phase	Definition
Pre-Treatment	Date ≤ Treatment Start Date
On-Treatment	Treatment Start Date < Date ≤ Treatment Stop Date + 1 day
Post-Treatment	Date > Treatment Stop Date + 1 day
Post-Randomization	Randomization Date < Date

NOTES:

If the treatment stop date is missing and the treatment start date is non-missing and Date > Treatment Start Date, then the assessment will be considered to be On-Treatment

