10.6.3. Efficacy

10.6.3.1. Hemoglobin Endpoints

Hemoglobin Values
Central Laboratory and HemoCue Hgb Values

 When source of Hgb measurement is not specified: 
 For reporting purposes, central laboratory Hgb values will be used, unless otherwise specified. However, if a central laboratory Hgb value is missing, a corresponding non-missing HemoCue Hgb value will be used. This approach will be used for the primary Hgb analysis. Some displays may be created for either central laboratory Hgb values only or HemoCue Hgb values only. The central laboratory summary will be considered the primary summary in this case.
Evaluable Hemoglobin Values

 Evaluable Hgb values are on-treatment Hgb values (see Section 10.4.1.1) that are not taken within the 8 weeks following a red blood cell transfusion, a whole blood transfusion, or a non-randomized ESA treatment which occurs on or after the randomization date. Red blood cell transfusions, whole blood transfusions and non-randomized ESA treatments occurring on or after the randomization date are identified by comparing the start and stop date of the respective transfusion or ESA concomitant medication record to the randomization date.
Imputed Hemoglobin Values

 For each missing value between baseline to Week 52 (inclusive), 200 imputed values will be generated using the multiple imputation method (see Section 7.1.2). The average of these 200 imputed values will be used as the value for this missing value in the summary tables and figures. For the primary efficacy Hgb analysis and the corresponding subgroup analyses using all available observed and imputed Hgb values (on and off-treatment), Rubin's rules [Rubin, 1987] will be used to combine results of the imputed datasets using SAS PROC MIANALYZE procedure.
EP Hemoglobin Value for Primary Hgb Analysis

 For each subject, the mean of all available (on and off treatment) Hgb values during the EP (See Section 10.6.1) including any imputed and unscheduled Hgb values that were taken during this time period. Should the assessment dates for Hgb values from the Early Treatment Discontinuation visit fall within the EP, then these values will be included as unscheduled Hgb values. Hgb values from the Follow-up visit will not be included in the EP mean.

CONFIDENTIAL

201410

Hemoglobin Values					

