EP Hemoglobin Value for While On-Treatment Evaluable Hgb Supportive Analysis					

 For each subject, the mean of all evaluable Hgb values during the EP (See Section 10.6.1) including any evaluable unscheduled Hgb values that were taken during this time period. Should the assessment dates for Hgb values from the Early Treatment Discontinuation visit fall within the EP, then these values will be included as unscheduled Hgb values. Hgb values from the Follow-up visit will not be included in the EP mean. 					
EP Hemoglobin Value for Alternative EP Supportive Analyses					

 For each subject, the mean of all Hgb values during the Alt. EP (See Section 10.6.1) including any imputed and unscheduled Hgb values that were taken during this time period. This analysis will be conducted using all available (on and off treatment) Hgb values and separately using evaluable Hgb values only. Should the assessment dates for Hgb values from the Early Treatment Discontinuation visit fall within the Alt. EP, then these values will be included as unscheduled Hgb values. Hgb values from the Follow-up visit will not be included in the Alt. EP mean. 					
Use of Unscheduled Hemoglobin Values and Multiple Hgb Values on the Same Date					

 The scenarios outlined below provide guidance on the use of unscheduled Hgb values and multiple Hgb values occurring on the same date. Each row represents a single calendar date. Rows outlining scenarios where there is at least one central lab Hgb and at least one HemoCue Hgb on the same date apply only for the derivation of Hgb values to be used in the primary Hgb analysis, where central lab values are used if they are available and if the central lab value is missing, then a corresponding non-missing HemoCue Hgb value is used. Rows outlining scenarios involving combinations of scheduled and unscheduled Hgb values of the same type apply to all Hgb summaries and analysis. 					
Scheduled Central Lab Hgb Value	Unscheduled Central Lab Hgb Value	Scheduled HemoCue Hgb Value	Unscheduled HemoCue Hgb Value	Value to Use	Type/Label
x				Scheduled central lab Hgb value	Scheduled visit
	x			Unscheduled central lab Hgb value	Unscheduled
		x		Scheduled HemoCue Hgb value	Scheduled visit
		multiple ¹		Average of scheduled HemoCue Hgb values	Scheduled visit
			x	Unscheduled HemoCue Hgb value	Unscheduled

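### The SAP does not say how ITT subjects without an evaluable on-treatment EP mean are counted in the Hgb responder analysis

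*SAP*

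**What the plan says.** - **Responder rule (SAP 8.1.2.2, Hgb Variability).** "Responders will be subjects with a mean Hgb during the EP that falls within the Hgb analysis range of 10-11.5 g/dL". For the mean itself, "mean Hgb during the EP will be defined as in the while on-treatment supportive analysis". Table 6 (SAP 8.1.2.1) gives the population as ITT and, in note 2, limits the data to evaluable values.
- **The mean (SAP 10.6.3.1).** It is "For each subject, the mean of all evaluable Hgb values during the EP". The definition reads "Evaluable Hgb values are on-treatment Hgb values (see Section 10.4.1.1) that are not taken within the 8 weeks following a red blood cell transfusion", and extends the 8-week rule to whole blood transfusion and non-randomized ESA treatment.
- **On-treatment window for Hgb (SAP 10.4.1.1).** "Treatment Start Date < Date ≤ Treatment Stop Date + 1 day".
- **Missing data in the while on-treatment analysis (SAP 7.1.2.5).** "No data will be imputed in this analysis, so a summary of missing data will be provided".
- **Display and test (SAP 8.1.2.2).** The summary by arm is "the number and percentage of subjects with mean EP Hgb above, within and below the Hgb analysis range". The arms are compared by a CMH test on the randomization strata and a Wald interval for the rate difference. The one-sided p-value is set against 0.025 as a nominal criterion.
- **Protocol.** Section 5.5 makes reaching the rescue criterion a mandatory reason for permanent discontinuation. Section 9.2.1 allows for up to about 30% stopping randomized treatment before Week 28.

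Neither document says how a randomized subject with no evaluable EP mean is classified in the responder analysis.

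**The concern.** A responder rate is normally read as the share of randomized patients who reached the target. Here the outcome is observed only in subjects who are still on randomized treatment in the EP and have at least one value outside the 8-week exclusion. Subjects stopped before Week 28 for persistently low Hgb are among those with no outcome. If they are left out of the denominator, some clear treatment failures are absent from a measure of treatment success, and the randomized comparison becomes a comparison of those who stayed on treatment.

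No planned companion analysis would show the effect. Week 52 Hgb change is run on all available values and again on evaluable values (Table 6, notes 1 and 2). The primary analysis was moved to all randomized subjects by multiple imputation (SAP 2.1, Table 1). Responders get the evaluable version only.

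**Working it through.** **1. Who has no mean.** The on-treatment window closes one day after the treatment stop date, and the EP opens at the Week 28 visit. A subject who stops more than a day before that visit, and does not restart, has no evaluable EP value. Transfusion or ESA use has a narrower effect. One transfusion at Week 26 removes values up to about Week 34, so the Week 28 and 32 visits are lost and the other five of the seven scheduled EP visits (36, 40, 44, 48, 52) remain. Losing the whole EP this way needs repeated events.

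**2. What the plan's own figures give.** Protocol 9.2.1 takes 30% of 150 as non-evaluable, leaving 105 per arm. With SD 1.5, the standard error is 1.5 × √(2/105) = 0.207, the 95% half-width is 0.408 and the limiting difference is -0.75 + 0.408 = -0.342, all as stated. Power by the non-central t is 95%, as in the table in Protocol 9.2.2. These figures concern the primary endpoint. The documents give no expected rate, power or sample size for responders, so every rate below is an assumption.

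**3. Effect on the rate.** If p is the rate among evaluable subjects and d the proportion without a mean, the rate over all randomized with a missing mean counted as non-response is p × (1 - d). With p = 60%:

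| d | Evaluable only | All randomized |
|---|---|---|
| 20% | 72/120 = 60% | 72/150 = 48% |
| 30% | 63/105 = 60% | 63/150 = 42% |
| 40% | 54/90 = 60% | 54/150 = 36% |

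**4. Effect on the arm difference.** With the same p in both arms, the evaluable-only difference is 0 and the all-randomized difference is p × (d for darbepoetin alfa - d for daprodustat). With p = 60%:

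- d = 30% in both arms: 0 under either rule.
- d = 35% daprodustat, 25% darbepoetin alfa: 0.60 × (0.25 - 0.35) = -6.0 points. In whole subjects, 59/98 v 67/112 is +0.4 points evaluable-only, and 59/150 v 67/150 is -5.3 points (95% CI -16.5 to 5.8).
- d = 40% v 20%: 54/90 v 72/120 is 0.0 points, and 54/150 v 72/150 is -12.0 points (95% CI -23.1 to -0.9).
- d = 20% v 40%: 0.0 becomes +12.0 points (95% CI 0.9 to 23.1). An unstratified one-sided test gives p = 0.50 under the first rule and 0.0176 under the second, so the counting rule alone can move the result across 0.025.

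**5. Which rule the SAP implies.** For exclusion: the display has only three classes and no missing class, and Table 4 (SAP 7.1.1) applies the ITT label to the non-imputed while on-treatment analysis, where a subject without a mean cannot contribute. For inclusion: SAP Section 4 defines ITT as everyone randomized, and a subject with no mean does not satisfy the responder definition. The text does not decide between them.

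**The case against.** The strongest reply is that a reader might infer that the plan drops early failures, and the documents do not say so. On a literal ITT reading these subjects are already non-responders. Elsewhere the SAP states when a value is undefined, as for percent time in range (10.6.3.1) and monthly IV iron (10.6.3.2), and it has no such clause for responders. Table 4 is not decisive either: an ANCOVA cannot use a subject with no continuous outcome, whereas a binary status can be assigned to anyone. This stands, and it makes the point an unstated rule rather than a demonstrated exclusion.

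Three further objections also stand in part.

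- The 30% is an upper planning figure for all permanent discontinuation. It includes transplant, pregnancy, cancer, liver criteria, prohibited medication and the subject's own request, so it must not be read as 30% efficacy failures. Subjects who fail during the EP normally keep their earlier evaluable EP values and remain in the analysis.
- A while on-treatment strategy is a declared choice. Counting a missing mean as non-response answers a different question, one that scores a transplant as poor Hgb control.
- Related information is planned elsewhere: a missing-data summary and evaluable-value exclusions by visit (7.1.2.5), time to stopping for rescue (8.1.2.2), and discontinuation reasons by arm (6.2.2). A careful reader could probably work out how many subjects lack a mean. The responder percentage and its test would still not carry that information, and two programmers could defensibly produce different results.

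**Conclusion.** The data source is explicit: evaluable on-treatment values with no imputation. The denominator is not. If subjects without a mean are left out, the response rate is conditional on staying on treatment, and its arm difference can be biased in either direction when discontinuation is unequal. Under an assumed 60% rate among evaluable subjects, the two rules differ by 12 to 24 points in the rate when 20% to 40% lack a mean. They differ by about 12 points in the arm difference for a 20-point imbalance, and by nothing when discontinuation and response are equal across arms.

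The documents do not support the stronger inferences that the SAP prescribes exclusion, that any transfusion or ESA use removes a subject, or that the result would favour daprodustat. The endpoint is an additional secondary one, nominal and unadjusted for multiplicity, and the primary Hgb analysis is unaffected. The change is worth making because it is cheap.

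**What to change.** In SAP 8.1.2.2:

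1. State the denominator of the responder rate.
2. Run the CMH test and the risk difference in all ITT subjects, counting those without an evaluable EP mean as non-responders, and present the evaluable-only analysis beside it.
3. Add a row by arm to the above/within/below table for subjects with no evaluable EP mean.

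The cost is about one sentence and one table row, with no new data. The downside is lower reported rates in both arms, and some discontinuations unrelated to efficacy, such as transplant, will count as non-response. For that reason both versions should be shown.

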8.1.3. Exploratory Efficacy Analyses

8.1.3.1. Overview of Planned Exploratory Efficacy Analyses

Table 7 provides an overview of the planned exploratory efficacy analyses.

Table 7 Overview of Planned Exploratory Efficacy Analyses

Endpoint	Analysis Population	Absolute				Change from Baseline			
		Summary		Individual		Summary		Individual	
		T	F	F	L	T	F	F	L
Hgb Variability									
Hgb observed (including imputed) and change from baseline (CFB) cross all visits to end of treatment	ITT	Included with Hgb primary and supportive analyses (Section 7.1)							
% of time Hgb is above, within and below Hgb analysis range (10-11.5 g/dL) during EP	ITT	Included with Hgb secondary analyses (Section 8.1.2)							
Number (%) of subjects with mean Hgb above, within and below Hgb analysis range during EP and at the end of treatment	ITT	Included with Hgb secondary analyses (Section 8.1.2)							

CONFIDENTIAL

201410

Endpoint	Analysis Population	Absolute				Change from Baseline			
		Summary		Individual		Summary		Individual	
		T	F	F	L	T	F	F	L
Number (%) of subjects with Hgb < 7.5 g/dL during EP ¹	ITT	Y							
Number of times Hgb < 7.5 g/dL during EP ¹	ITT	Y							
Number (%) of subjects with a >1g/dL increase in Hgb over 2 weeks (assessed at Week 2 and Week 4) or a >2 g/dL increase in Hgb within any 4 week period from Week 4 to Week 52 ¹	ITT	Y							
Number (%) of subjects with a >1g/dL decrease in Hgb over 2 weeks (assessed at Week 2, Week4, Week6, and Week 8) or a >2 g/dL decrease in Hgb within any 4 week period from Week 4 to Week 52 ¹	ITT	Y							
N(%) of subjects with a Hgb value ≥ 12 g/dL during the EP ¹	ITT	Y							
Number of times Hgb ≥ 12 g/dL during the EP ¹	ITT	Y							
% of time Hgb ≥ 12 g/dL during the EP ¹	ITT	Y							
Iron Parameters									
Hepcidin, ferritin, TSAT, total iron, TIBC observed and CFB cross all visits to end of treatment	ITT	Y	Y			Y	Y		
Average quarterly IV iron dose/subject	ITT	Y	Y						
Average quarterly TSAT	ITT	Y	Y						
Average quarterly ferritin	ITT	Y	Y						
Subjects who met iron management criteria	ITT	Y							
RBC and Whole Blood Transfusions									
Number (%) of subjects receiving at least one RBC or whole blood transfusion by Week 52	ITT	Y							
Number of RBC and whole blood transfusion events per 100 patient years	ITT	Y							
Number of RBC and whole blood transfusions per 100 patient years	ITT	Y							
Number of RBC and whole blood units per 100 patient years	ITT	Y							
Time to first RBC or whole blood transfusion	ITT	Y	Y						
Dose Adjustment Scheme Evaluation									
Assigned dose by visit	ITT	Y	Y						

CONFIDENTIAL

201410

Endpoint	Analysis Population	Absolute				Change from Baseline			
		Summary		Individual		Summary		Individual	
		T	F	F	L	T	F	F	L
Most recent dose by visit	ITT		Y						Y
Number (%) of subjects with 0,1,2, or >2 dose adjustments during the following periods Day 1 - <Week 28, Week 28 -< Week 52, Day 1 - < the end of treatment	ITT	Y							
Number of dose adjustments during the following periods: Day 1 - <Week 28, Week 28 -< Week 52, Day 1 -< the end of treatment	ITT	Y							
Time dose held for Hgb \geq 12 g/dL	ITT	Y							

NOTES :

- T = Table, F = Figure, L = Listing, Y = Yes display generated.
 - Summary = Represents TFL related to any summaries (i.e. descriptive statistics) of the observed raw data.
 - Individual = Represents FL related to any displays of individual subject observed raw data.
- ⁽¹⁾ Summaries will be presented using evaluable Hgb values only (see Section 10.6.3).

